- (3) Patients who should undergo other long-term merger resection during distal gastrectomy. (except cholecystectomy)
- (4) Patients with significant ascites by CT.
- (5) Patients with cirrhosis in CT brfore surgery
- (6) Patients with heart disease (history of uncontrolled hypertension, angina or coronary artery disease, history of cardiac muscle disease, Ejection Fraction <50%)
- (7) Patients with inappropriate renal function (serum creatinine > 1.4 mg/dL or BUN > 26 mg/dL)
- (8) Patients with abnormal coagulation (PT INR > 1.2 or aPTT > 45 sec)
- (9) Uncontrolled diabetic patients
- (10) Inflammatory bowel disease patients including Crohn's disease, ulcerative colitis, tuberculous enteritis
- (11) Patients taking aspirin or platelet inhibitors within 5 days before surgery
- (12) Patients taking anticoagulants

- (13) Patients with the history of steroid use which needs stress dose inoculation
- (14) Pregnancy
- (15) Other patients who are deemed unable to participate in the clinical trial by the tester
- (16) History of sensitivity to iodine, in case the test using indocyanine green is applied
- (17) Previous history of gout

3) Target number of subjects and basis of calculation

Total target number: 189, competitive enrollment at SNUH and SNUBH Calculation methods of the subjects

Primary evaluation variable: Cerum CRP value on Post-op 2nd day **Subjects of the study**

Main analysis group

- A. Ultrasonic shears
- B. Bipolar sealing device

Explorative analysis group

C. Hybride device

Study hypothesis:

- Null hypothesis: No difference in CRP value on post-op 2nd day between two groups.
- Alternative hypothesis: Difference in CRP value on post-op 2nd day between two groups.

Hypothesis for calculation of number of subjects:

- (1) Level of significance, $\alpha = 0.05$
- (2) Ratio between groups, group A: group B = 1:1
- (3) Type 2 error (β) is 0.20, retaining power of the test at 80%
- (4) Ultrasound dissector and Bipolar's post-op's CRP average and standard deviation was 11.5 ± 6.6 and 8.0 ± 2.8 from preceding research of "Research of availability and safety in using Articulating bipolar vessel sealer system in early Robotic gastrectomy in early stage gastric cancer". Subjected patients were 17, small in numbers and it was for Robotic LAP surgery, not conventional LAP surgery. Therefore, to avoid chances for reflecting not enough subjected patients, we have calculated subjected patient numbers from conservative standard deviation.

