- 16) Endocrine: Diabetic ketoacidosis, hyperglycemic hyperosmolar state, Addison's disease, hypothyroidism, etc. Clinically diagnosed
- 17) Stasis: Refers to the case where food is obstructed to pass through the anastomosis, even though there is no evidence of intestinal obstruction, stenosis, leakage, or peritonitis.

- 18) Pancreatic leakage: A case when the amylase level of the drain tube 3 days or more after surgery exceeds 540 U/L, which is three times the normal maximum value of 180 U/L of the normal blood test (1, 3, Check on day 5).
- 19) Chylous ascites: Suspected when the color of a clear white fluid is found with the naked eye, and JP diagnoses that triglyceride is 110 mg/dL.
- 20) Deep Vein Thrombosis
- 21) Central venous infections

9) Evaluation standards, evaluation methods and analysis methods (statistical analysis methods, etc.)

- (1) Primary endpoint: Two days after surgery, serum CRP
- ; Student's t test or ANOVA test was performed by using the mean of CRP value on the second day between the three groups.
- (2) Secondary endpoint:
- Blood loss during operation (ml), amount of blood transfusion (pint); Output-input (ml). Gauze measures the total weight of gauze used during surgery and calculates the difference from the gauze weight measured before surgery. Inhalation volume is calculated by subtracting the amount of 0.9% physiological saline solution applied to the surgical site from the total inhalation volume.
- Serum IL-6, IL-10

Serum IL-6 and IL-10 levels were measured at baseline immediately after general anesthesia and insertion of the trocar. The mean value of serum IL-6 and IL-10 levels 2-3 hours after the operation, the 2nd postoperative day, and the 4th postoperative day are compared by Student's t test or ANOVA test.

- Amount of remaining ICG: Total amount of the remaining ICG will be calculated by the mean value of concentration of the ICG measuring 3 sets for each patient multiplied by 500 (ml) (600 or 700 ml for corresponding cases), and the mean value of the amount of ICG will be compared between each group using t test.

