- Complications and mortality rate within 30 days after surgery: Clavien-Dindo classification is used to grade the complications of the three groups and the $\chi 2$ test is performed using the Cross Table for the frequency of complications and Grade IIIa complications. For the total complications, the Student's t test or the ANOVA test was performed using the Comprehensive Comorbidity Index between the three groups.

- After 4 days postoperatively, serum CRP, amylase, serum/ascites triglyceride: The preoperative mean value was used as the baseline and the Student's t test or the ANOVA test was performed on the mean value of the three groups at the 4th postoperative day
- Post-operative pain medication frequency: Student's t test or ANOVA test is performed on the average daily frequency of use among the three groups of non-PCA narcotic analgesics.
- Postoperative visual pain score (VAS score): The mean postoperative VAS score between the three groups is verified by Student's t test or ANOVA test.
- Post-operative transfusion, gas evacuation, liquid diet initiation: If the postoperative Hb < 8, transfusion can be performed under the judgment of the tester and record transfusion. The mean number of days from the day of surgery was verified by Student's t test or ANOVA test among the three groups.
- Length of hospital stay: The average number of days between surgery and discharge is assessed by Student's t test or ANOVA test among the three groups.
- Re-admission, emergency room visit: Within 30 days from the date of surgery, record admission / visit and evaluate complications if you are re-admitted to the hospital or visited the emergency room.
- A new version of the harmonic scalpel was introduced during the research and the target of the ultrasonic group is being studied with a new product. (Since IRB approval in July 2018)
- We will compare the results of the patients who underwent surgery in the ultrasonic group regarding to old instrument versus new instrument. In the comparison between the groups, it will be analyzed whether there is a difference between the inclusion and the non-inclusion of the subject who underwent surgery with the old apparatus. In these ways, it will be notated in the final report whether there is any influence on the results of the study by the change of the device.

9-1) General principles of statistical analysis.

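### The CRP tests named assume equal variances; if the pilot SDs carry over, the planned comparison without old-device patients would reject too often, while the balanced A versus B t test would not

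*Combined protocol and SAP*

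**What the plan says.** **Test.** Section 11, part 9)(1), gives the primary analysis of day-2 CRP across the three groups: "Student's t test or ANOVA test was performed by using the mean of CRP value on the second day". It does not choose between the two tests. Part 9-1) again names Student's t for group differences, with the Wilcoxon rank-sum test as alternative, and sends data that fail parametric assumptions to a non-parametric test. It gives no criterion for that switch. It also says that an SAP will be written before database lock.

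**Variance data.** Section 10, part 3), is the only source: "Ultrasound dissector and Bipolar's post-op's CRP average and standard deviation was 11.5 ± 6.6 and 8.0 ± 2.8". It adds a caution: "Subjected patients were 17, small in numbers and it was for Robotic LAP surgery, not conventional LAP surgery". For sample size the larger SD is used in both arms: "we have calculated subjected patient numbers from conservative standard deviation".

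**Device change.** Section 11, part 9)(2), reports that a new version of the ultrasonic instrument came into use during the trial. It plans to examine whether the group comparison differs between "the inclusion and the non-inclusion of the subject who underwent surgery with the old apparatus", and to state any influence in the final report. The number of old-device patients is not given.

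**Roles of the arms.** The hypothesis in section 10, part 3), concerns two groups, A and B. Group C (hybrid) is exploratory. Allocation is 1:1:1.

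**The concern.** Student's t and ordinary ANOVA estimate one common variance. The pilot SDs of 6.6 and 2.8 give a variance ratio of (6.6/2.8)² = 5.6. Such a difference does little harm when the two arms are the same size. It does harm when the arm with the larger SD is the smaller arm: the pooled variance is then dominated by the less variable arm, the standard error is too small, and the test rejects too often. Removing old-device patients creates that situation, because all of them are in A, the arm with the larger pilot SD.

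A related problem arises if ANOVA is used to test A against B on the three-arm error term. Group C's variance then enters the standard error of a contrast to which C does not belong, and equal arms do not cure that.

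At stake is the statement promised for the final report on whether the device change affected the results, and the A versus B p value if it is taken from a pooled ANOVA contrast.

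**Working it through.** **Inputs.** SDs of 6.6 (A) and 2.8 (B), a difference of 3.5 (11.5 − 8.0), α = 0.05, 80% power and 57 per arm are from section 10, part 3). A two-sided test is inferred from the alternative hypothesis. The number left in A after removal and the SD in C are assumptions, so ranges are shown.

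**1. The plan's own figure.** Normal approximation: n = 2(1.96 + 0.842)² × 6.6² / 3.5² = 55.8, so 56 per arm. The noncentral t version gives 56.8, so 57, as stated. For the total, 57/0.9 × 3 = 190, against 189 (3 × 63) in the plan, which is a rounding difference.

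**2. Why imbalance matters.** The true variance of the mean difference is 6.6²/nA + 2.8²/nB. Student's t estimates it by s²(1/nA + 1/nB), where on average s² = [(nA − 1)6.6² + (nB − 1)2.8²]/(nA + nB − 2).

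- At 57 and 57 both expressions equal 0.902, so the test is protected.
- At 40 and 57 the true variance is 43.56/40 + 7.84/57 = 1.227. The pooled s² is (39 × 43.56 + 56 × 7.84)/95 = 22.50, which gives 22.50 × (1/40 + 1/57) = 0.957. The variance is understated by 22%.

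**3. Type I error by simulation** (normal data, equal means, SDs 6.6 and 2.8, 57 in B):

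| Left in A | Student's t | Welch's t |
|---|---|---|
| 57 | 5.2% | about 5% |
| 50 | 6.2% | about 5% |
| 40 | 8.5% | about 5% |
| 30 | 11.7% | about 5% |
| 20 | 16.8% | about 5% |

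Repeat runs with other seeds differ by a few tenths of a percentage point at most.

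**4. Sensitivity to the SDs.** With 40 in A and 57 in B, Student's t gives 7.7% if B's SD is 3.5, 6.6% if 4.5, 5.7% if 5.5, and 5.0% if it equals A's 6.6.

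**5. The fallback.** At SDs 6.6 and 2.8 with 57 in B, the Wilcoxon test rejects in about 6.1% (57 in A), 7.9% (40) and 9.0% (30) of null trials. It does not restore 5%.

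**6. ANOVA contrast on a common error term, 57 per arm.** The correct variance for A versus B is the mean of the two arms' variances, (43.56 + 7.84)/2 = 25.70. The ANOVA error term is (43.56 + 7.84 + SD²)/3, with SD that of C.

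| SD in C (assumed) | Error term | A versus B | A versus C | B versus C |
|---|---|---|---|---|
| 2.8 | 19.75 | 8.6% | 8.6% | 0.2% |
| 5.07 | 25.70 | 5.0% | 9.1% | 1.6% |
| 6.6 | 31.65 | 3.0% | 9.5% | 3.1% |

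The overall three-group F test lies between 5.5% and 6.6% over this range. Pairwise t tests that use only their own two variances stay at about 5% with equal arms.

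**The case against.** **The powered comparison is sound.** The hypothesis is A versus B with equal allocation, and Student's t is then at about 5.2% even with the pilot SDs. This stands. A reader might infer that the primary result is invalid; the documents do not support that when the primary test is run as a two-sample t test on arms of equal size.

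**The plan names no pooled A versus B contrast.** The wording can be read as a t test for two groups and an overall F test for three. This also stands, so the ANOVA part of the point is conditional. A reader might further infer that every three-arm ANOVA contrast is wrong. That is not so: A versus B is at 5.0% if C's SD is about 5.1. No SD for C is given. The protocol does expect the hybrid to behave like the ultrasonic device, which would point towards the 6.6 row and a conservative A versus B contrast.

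**The plan has a fallback.** It does, but it has no trigger, it is off level for these SDs, and it moves away from the difference in means on which the trial was sized.

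**The SDs are weak evidence.** They come from 17 robotic patients, which the protocol itself treats with caution, and they were observed at different means. If the SD scales with the mean (an assumption), B's SD under the null would be about 11.5 × 2.8/8.0 = 4.0, and the error falls to about 7.0% with 40 in A and 8.9% with 30. This limits the size of the problem but does not remove it.

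**Welch is not exact either.** With assumed lognormal data of mean 11.5 and the same SDs, it gives 6.0% at 40, 6.2% at 30 and 6.9% at 20. It is still much closer to 5% than Student's t is at those sizes under normal data.

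**Conclusion.** The point holds in a conditional form. If the ultrasonic arm is as variable relative to the bipolar arm as in the pilot, the comparison without old-device patients, analysed by Student's t, has a type I error above 5%: about 6.2% with 50 left in A and 16.8% with 20, with 57 in B. The true position in that range is unknown because the number of old-device patients is not stated. The excess shrinks as the SDs converge and disappears when they are equal. The Wilcoxon fallback does not cure it. An A versus B contrast on a three-arm error term, if one is used, could range from 3.0% to 8.6% for the SDs of C examined.

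The documents do not support saying that the error rate is wrong outright, or that the balanced A versus B t test is affected. What is exposed is a planned sensitivity analysis and an ANOVA option that the plan leaves open. The severity is minor to moderate.

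**What to change.** In the SAP, before database lock:

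- Name Welch's t test for A versus B, or linear regression with heteroscedasticity-robust standard errors, using only the A and B variances. Apply it to the full comparison and to the comparison without old-device patients.
- For any comparison involving C, use contrasts that allow unequal variances instead of a common ANOVA error term.
- Remove the open choice between Student's t and ANOVA for the primary endpoint. If the Wilcoxon test is kept, make it a pre-stated supporting analysis and not an untriggered replacement.
- Report the number of old-device patients and the SD in each arm, so that a reader can judge the imbalance.

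The cost is a few sentences. At the planning values (57 per arm, SD 6.6 in both, difference 3.5) simulated power is 80.0% for both Student's t and Welch's t, so the sample size does not change.

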item Pre-Op (Baseline			Intra-		PC	DD (Post	Operativ	1st outpatient visit after discharge	End of study/ Early termination		
	(Baseline)	abdomen	Ор	2-3hr	#1	#2	#3	#4	Discharge		
Informed consent ¹	✓										
Selection/exclusion criteria	√										
Demographic information	✓										
History, ASA	✓										✓
Physical examination, weight	*										√
Random assignment		✓									
Lab (cbc, admission panel, amylase, CRP², triglyceride³)	*					*		✓		(✔)	
Blood cytokine ⁴		✓		*		1		1			
JP drain amount					1	1	1				
JP drain TG, amylase						1					
ICG concentration ⁵			✓								
Operation ⁶											
Blood volume			✓								✓
Operation time			✓								✓
Amount of blood transfusion			✓								✓
Surgical information			✓								✓
Analgesic medication (excluding PCA)					√	✓	*	√			
VAS pain score	*				1	✓	1	1			
Gas out day									✓		
Soft diet starting date									✓		
EGD, EUS,CT	✓										
Hospital stay count									✓		✓
Pathologic result confirmation	1								✓	*	
Adverse events ⁷			✓	✓	*	√	✓	✓	*	1	✓
Follow-up visit		_								1	

All procedures, including selection / exclusion criteria, may be initiated after voluntary written consent has been obtained from the subject. If surgery is not performed within thirty days after obtaining the consent form, the procedures for rehabilitation shall be carried out.

CRP was further examined within 2 days before surgery

Triglyceride is examined by the researcher's option on the first outpatient visit after discharge

After patient anesthesia in the surgical field, blood is drawn through the A-line.

Only for Seoul National University Hospital

Surgery is performed according to standard surgical guidelines.
 Adverse events are evaluated up to POD # 30.

4-1) Baseline before surgery

- 1) Subject consent form
- 2) Demographic information
- 3) Detailed medical history
- 4) Significant medication or operation history
- 5) Physical examincation
- 6) Laboratory test: CBC, PT, aPTT, BUN, Triglyceride, Albumin, Total bilirubin, Creatinine, CRP, Amylase, use the test results within 30 days before surgery
- 7) Concomitant medication (including drugs within the past week)
- 8) EGD, EUS, CT use test results within 2 months from the scheduled date of surgery.
- 9) Measure VAS score on the day before surgery.

4-2) operation day

- 1) Randomization: prior to surgery.

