A multivariable analysis of primary and primary secondary efficacy variables is performed. Multivariate analysis uses multiple linear regression models or multiple logistic regression models depending on the type of outcome variable. The main independent variable is the test, we will include the gender and stage of the stratified variables used in randomization in the model and the perturbed variables identified in the demographic and clinical history data analyzes to control the effect. For repeated measurement data, perform a multivariate analysis using the generalized estimation equation (GEE). If a significant interaction effect is found between the treatment group and the participating laboratories and / or the treatment group and the confounding variables, the effect is controlled by including the interaction term in the multivariate model.

• The content of the pre-planned subgroup analysis to be performed in this trial is as follows:

- Gender Male Female)
- BMI (<25 / ≥25)
- Cancer stage (TNM stage)
- Operator
- In vitro / Internal Anastomosis
- The differences between the groups were assessed using the Student's t-test (or the corresponding nonparametric Wilcoxon rank-sum test) or the χ2 test (or Fisher's exact test, the corresponding nonparametric method) Analysis. If control of disturbance variables is required, multivariate analysis is performed.

9-2) Treatment of missing values.

In general, the missing value will be treated as a missing state, and no alternative missing statistic is used. Therefore, only observations will be used for data analysis. Discrepancies data are replaced by missing values at the responsibility of the clinical trial manager.

10) Clinical trial and treatment standard

The same type of treatment and treatment will be given to patients with general gastric cancer who are being treated at Seoul National University Hospital.

11) Study Schedule

- 42 months after IRB approval: registration of clinical trial subjects and clinical trials
- 42 months ~ 48 months: Data analysis and presentation

12. Data and Safety Monitoring Plan

1) The person in charge of monitoring

- * Monitoring supervisor: [name], Associate Professor, Surgery, Seoul National University Hospital
- * Person in charge of monitoring: [name], Department of Nurse, Seoul National University Hospital

2) Data and safety information monitoring items

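### Minor free improvement: the primary comparison of POD 2 CRP is unadjusted, although each patient's own pre-operative CRP is collected and could be a prespecified covariate

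*Combined protocol and SAP*

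**What the plan says.** - **Primary test.** Section 11, item 9)(1) specifies a Student's t test or ANOVA "using the mean of CRP value on the second day between the three groups". No covariate is named.
- **Baseline CRP.** Section 10, item 1), criterion (7) admits only patients with a pre-operative CRP of 1.0 mg/dl or less. A footnote to the schedule in Section 11, item 4) adds that "CRP was further examined within 2 days before surgery".
- **POD 4 CRP.** For this secondary endpoint, item 9)(2) does mention a baseline: "The preoperative mean value was used as the baseline".
- **Adjusted model.** Item 9-1) plans a multiple linear regression of the primary variable, without making it the primary test. Its covariates are gender and stage, described there as the stratification variables, plus "perturbed variables identified in the demographic and clinical history data analyzes". Baseline CRP is not named.
- **Stratification.** Section 11, items 1) and 2) stratify randomization by institute and by intracorporeal or extracorporeal anastomosis, not by gender and stage.
- **Missing data.** Item 9-2) uses observed values only, without imputation.

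**The concern.** A versus B on POD 2 CRP is the only comparison the trial was sized for. A pre-operative measurement of the same analyte is the natural covariate for it. Adjusting for that value lowers the residual variance to whatever extent it predicts the outcome, and removes chance baseline imbalance from the estimate.

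The regression in item 9-1) does not reliably supply this adjustment. It is not the primary analysis. Its further covariates are to be found in demographic and history data after the data have been seen, and a laboratory baseline is not clearly among them. The plan gives POD 4 CRP a baseline but gives none to POD 2 CRP, the primary endpoint.

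At stake is a small amount of power, and a primary model fixed in advance.

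**Working it through.** **Inputs from the documents** (Section 10, item 3)): means 11.5 and 8.0, so a difference of 3.5; SD 6.6 in both arms; alpha 0.05; target power 80%; "group A: group B = 1:1". The test is taken as two-sided because the alternative is non-directional: "Alternative hypothesis: Difference in CRP value on post-op 2nd day between two groups".

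**Assumptions.** The baseline to POD 2 correlation r is not in the documents. No unit is given with the sizing figures; mg/dl is assumed, the unit of the entry criterion.

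**Step 1: reproduce the plan.** Noncentral t, n per arm, noncentrality = 3.5 / (6.6 × √(2/n)). Power is 79.4% at n = 56 and 80.1% at n = 57. The stated 57 per arm reproduces. For dropout, 57/0.9 × 3 = 190; the stated 189 follows from rounding 63.3 per arm down to 63.

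**Step 2: what the entry cap implies for r.** A baseline confined to 0 to 1 mg/dl has an SD of at most 0.5, or about 0.29 if spread uniformly. With slope b (POD 2 CRP per 1 mg/dl of baseline), r = b × baseline SD / 6.6. The slopes of 1 to 3 are assumed.

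- Baseline SD 0.29: b = 1 gives r = 0.04, b = 3 gives r = 0.13.
- Baseline SD 0.5 (the ceiling): b = 1 gives r = 0.08, b = 3 gives r = 0.23.

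**Step 3: power after adjustment.** Residual SD = 6.6 × √(1 − r²), 57 per arm, one degree of freedom fewer. Equivalent n per arm is 57/(1 − r²).

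| r | Residual SD | Power | Equivalent n per arm | Slope needed if baseline SD is 0.29 |
|---|---|---|---|---|
| 0 | 6.60 | 80.1% | 57.0 | 0 |
| 0.04 | 6.59 | 80.2% | 57.1 | 0.9 |
| 0.13 | 6.54 | 80.8% | 58.0 | 3.0 |
| 0.23 | 6.42 | 82.2% | 60.2 | 5.2 |
| 0.3 | 6.30 | 83.7% | 62.6 | 6.8 |
| 0.4 | 6.05 | 86.5% | 67.9 | 9.1 |

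The range 0.04 to 0.23 therefore gains about 0 to 2 percentage points. Even at the ceiling SD of 0.5, r = 0.3 needs a slope of 0.3 × 6.6/0.5 = 4.0.

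**Step 4: chance imbalance.** At baseline SD 0.29, the standard error of the A minus B baseline difference is 0.29 × √(2/57) = 0.054 mg/dl. A slope of 3 turns this into about 0.16, against a target difference of 3.5.

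**Step 5: cost.** Baseline CRP uses one degree of freedom. Institute and anastomosis type, two levels each, use two more. With all three and no predictive value at all, power is still 80.1%. A lost patient matters more: at r = 0.1, power is 80.5% with 57 per arm but 79.8% with 56, below the unadjusted 80.1%.

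**The case against.** The strongest case against is that nothing here is wrong. The unadjusted test is unbiased under randomization and is the test the sample size assumes. The gain depends on a correlation the documents do not give, and the entry cap holds it down. Item 9-1) already plans an adjusted regression and leaves detail to an SAP written before database lock. All of this stands, and it limits the point to a minor one. It does not remove the point, because the planned regression neither names baseline CRP nor serves as the primary test.

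A second objection is that adjustment is not free if patients drop out of the model. This also stands. Under the observed-data rule, one missing 2-day value per arm could cancel the gain, so the fix needs a fallback value.

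Stronger readings that a reader might infer, and that the documents do not support:

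- *The trial lacks power without adjustment, or has no margin.* It reaches its stated power unadjusted. Section 10, item 3) also applied the larger of two observed SDs (6.6 and 2.8) to both arms as a conservative choice. With the pooled value √((6.6² + 2.8²)/2) = 5.07, power at 57 per arm is about 95%, though that source had only 17 patients.
- *Adjustment is worth several patients per arm.* Correlations of 0.2 to 0.3 would be worth about 2 to 6 per arm (57/(1 − r²) = 59.4 and 62.6). At baseline SD 0.29 they need slopes of about 4.6 to 6.8, which nothing in the documents supports.
- *The POD 4 analysis ignores patients' own baselines.* The wording on the pre-operative mean is ambiguous and may be loose translation. It needs clarifying, but does not establish this.

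**Conclusion.** The point holds as a minor, optional improvement in efficiency. The primary analysis leaves unused a covariate that is already collected, and using it would probably raise power from 80.1% to between 80.2% and 82.2% at 57 per arm. The validity of the unadjusted test is not in question.

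The size rests on three assumptions: a correlation of 0.04 to 0.23, which itself comes from assumed slopes of 1 to 3; a baseline SD between 0.29 and its ceiling of 0.5; and POD 2 CRP in mg/dl. If the sizing figures were in mg/L, baseline SD could reach 5, the cap would restrict the correlation much less, and the gain could be larger.

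One textual matter is firmer than the power gain: item 9-1) names gender and stage as the stratification variables, while Section 11, items 1) and 2) name institute and anastomosis type. The same edit can settle it.

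**What to change.** 1. In Section 11, item 9)(1), and in the SAP, prespecify the primary A versus B analysis as a linear model of POD 2 CRP on device, adjusting for the patient's own pre-operative CRP, institute and anastomosis type.
2. Define the baseline as the value from within 2 days before surgery or, if that is missing, the latest earlier pre-operative value, so that no patient is lost under item 9-2).
3. In item 9-1), replace gender and stage as the named stratification variables with institute and anastomosis type.
4. Keep the unadjusted t test as supportive, and say how the nonparametric fallback in item 9-1) relates to the linear model.
5. Use the same model for POD 4 CRP, and make clear that the baseline in item 9)(2) is each patient's own value.

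The cost is a change of wording before database lock and three degrees of freedom. No new data and no change to the sample size are needed.
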